#### **Recist Criteria**

Complete Response (CR)	Disappearance of all target lesions
Partial Response (PR)	At least a 30% decrease in the sum of the longest diameter (LD) of target lesions, taking as reference the baseline sum LD.
Progressive Disease (PD)	At least a 20% increase in the sum of the LD of target lesions, taking as reference the smallest sum LD recorded since the treatment started or the appearance of

	one or more new lesions.
Stable disease (SD)	Neither sufficient shrinkage to qualify for PR nor sufficient increase to qualify for PD, taking as reference the smallest sum LD since the treatment started.

## **10. Removal of Patients from Study/Off Study Criteria**

In the absence of treatment delays due to adverse events, treatment may continue until one of the following criteria applies:

- a) Intercurrent illness that prevents further administration of treatment,
- b) Patient decides to withdraw from the study,
- c) Noncompliance with treatment plan,
- d) General or specific changes in the patient's condition render the patient unacceptable for further treatment in the judgment of the investigator,
- e) Protocol violation - any patient found to have entered this study in violation of the protocol might be discontinued from the study at the discretion of the Principal Investigator.

## **11. Laboratory Evaluations and Procedures/Correlative and Pharmacokinetic Studies**

### **11.1 An overview of the possible molecular investigations, and in order of priority include**

1. FoundationOne genomic profile from paraffin embedded tumor samples taken before cetuximab, before/at definitive local treatment and after progression
2. Analysis of ADCC and caspase by IHC
3. RNA sequencing of tumor samples before and after cetuximab
4. RNA sequencing of skin samples before and after cetuximab
5. DNA sequencing of tumor and skin samples before and after cetuximab
6. IHC analysis of EGFR downstream pathways that are illuminated by the above

The laboratory investigations are very comprehensive, ranging from partial DNA sequencing (FoundationOne™) in order to check for a battery of known DNA mutations related to cancer, to RNA sequencing on fresh tissue, which will shed light on how protein production is altered when the tumor is treated with cetuximab. FoundationOne™ is targeted DNA sequencing that is performed on paraffin embedded tumor samples. As a pan-cancer test, FoundationOne™ is designed to interrogate the entire coding sequence of 236 cancer-related genes (3,769 exons) plus 47 introns from 19 genes often rearranged or altered in cancer. These genes are known to be somatically altered in human solid cancers based on recent scientific and clinical literature. ADCC and caspase will be examined

by IHC as in the laboratory, using paraffin embedded tissue from pre- and post- treatment samples. In addition, RNA sequencing will be performed on tumor samples from before and after neoadjuvant cetuximab, to investigate changes in protein production caused by cetuximab ie changes in protein production downstream in the EGFR pathway or completely alternate pathways that may be triggered by cetuximab. Western blot will also be utilized to look at changes in protein production in the EGFR pathway and other relevant signaling pathways. In addition, HPV status can be easily determined from RNA sequencing. Once the cDNA library is created by the Cancer Institute Functional Genomics ([name] and, [name]), analysis will be performed by bioinformatics. We will have experience with the procedures necessary to perform these analyses that are ongoing in protocol CINJ #091305. In addition, these complementary protocols will allow us to conduct parallel investigations in squamous tumors of the skin versus those of the head and neck, and to see if similar mechanisms are operative or if in fact these tumors are distinct biologic entities.

## **11.2 Tissue to be collected**

All patients must have a diagnosis of squamous cell carcinoma (SCC) of skin prior to entering into this protocol. This diagnosis is typically achieved by a biopsy from either the primary site or FNA from a neck lymph node. However, the scant amount of tissue obtainable from an FNA would not be adequate for the molecular biology aspect of this protocol, which include

1. Providing tissue to the pathology department so that they are able to confirm diagnosis of SCC in the tissue retrieved, which then will be sent to FoundationOne™ for DNA sequencing and analysis of genetic mutations.
2. Providing frozen tumor to the Cancer Institute Functional Genomics Facility for RNA sequencing
3. Providing frozen tumor and skin tissue to be used in Western Blot analysis.
4. Providing FFPE tumor and skin tissue for use in IHC analysis.

Thus, all patients on the protocol, prior to neoadjuvant cetuximab, will have an incisional/core biopsy from the primary site and a skin punch biopsy even though they already have a diagnosis of SCC. Incisional biopsy is favored over other types (core biopsy) for this biopsy because incisional biopsy has the best chance of supplying an adequate tumor sample.

After neoadjuvant cetuximab, additional tissue will be obtained at surgery or if the patient is not a candidate for surgery, biopsy will be obtained prior to treatment with XRT or with further systemic therapy. This tissue will only be used for RNA sequencing (and not sent to FoundationOne™ for DNA analysis), and thus a core biopsy may be employed here instead of incisional biopsy. A skin punch skin biopsy will also be performed after neoadjuvant cetuximab, preferably from a similar location as the first skin biopsy i.e. obtain two skin biopsies of neck and neck or right upper chest and right upper chest. If there is a locoregional/distant recurrence or persistence, a third incisional biopsy of locoregional/distant disease if possible and again paraffin-embedded sample will be sent to FoundationOne™ for analysis and fresh tissue may be obtained for RNA sequencing.

## **11.3 Collection and Handling Procedures**

Collection and handling procedures will be performed at RWJUH, New Brunswick campus.

1. Prior to day of procedure, OHRS will be informed of the pending biopsies.  
Incisional or excisional biopsy will be obtained from the primary site and BRS notified.
2. Tissues will be sent to RWJUH pathology and research specimens will be transported by BRS
3. At RWJUH pathology
  - a. Part of the tumor sample will be made into a paraffin embedded block, part of which they will use to confirm SCC, and the remainder of the paraffin embedded block will be sent to FoundationOneTM.
  - b. Part of the tumor sample will be put in dry ice and sent asap to the Cancer Institute Genomic Facility ([name]).
  - c. The skin sample will be logged in, put in dry ice and sent asap to Cancer Institute Genomic Facility. The skin sample does not require any pathologic diagnosis, and its purpose is solely to investigate etiology of the cetuximab folliculitis.

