## 6. Study Parameters

Evaluations	Pre-cetuximab	Weekly during neoadjuvant cetuximab	Post-cetuximab (Week 9)	At surgery or prior to RT 	30 days after surgery or XRT	Follow ups every 3 months after surgery or XRT for 2 years	After locoregional or distant failure
History, physical exam and tumor site assessment	X  (within 14 days of treatment)	X 	X 		X 	X 	X 
Photo of tumor and/or rash at head, neck, upper torso put into EMR	X (within 14 days of treatment)	X 	X 				
Incisional/core biopsy of primary tumor and loco-regional lymph nodes if involved	X  (within 30 days of treatment)			X  (any time during this interval)			X (within 30 days of relapse)
Biopsy of skin	X  (within 30 days of treatment)			X  (any time during this interval)			X (within 30 days of relapse)
CBC, differential, platelets	X (within 14 days of treatment)	X			X	X	
Serum Chemistries 	X (within 14 days of treatment)	X	X	X	X	X	
Liver Enzymes 	X (within 14 days of treatment)	X			X	X	
Pregnancy Test 	X (within 14 days of treatment)						

Radiographic Assessments 	X  (within 30 days of treatment)		X 			X	X 
---------------------------------------	---	--	----------------	--	--	---	----------------

\*A +/- 2 day window is allowed for all study assessments indicated on this trial except treatment for which a +/- 1 day window is allowed.

1. To include toxicity assessment, ECOG performance status, weight
2. Includes: Electrolytes, including serum magnesium, potassium, Calcium, BUN, Creatinine, Glucose,
3. Includes: Total and Direct. Bilirubin, AST/ALT, Alkaline Phosphatase, Albumin, Total Protein.
4. Women 18-55 who have not undergone menopause must have urine pregnancy test within 14 days of enrollment.
5. Tumor assessments as indicated by investigator, i.e. PET/CT, CT neck, chest/abdomen and pelvis or MRI of neck as needed to be obtained no more than 1 month prior to cetuximab; then per standard of care, in general, every three months after conclusion of surgery or XRT.
6. Every 7 days
7. Includes evaluation by surgery and radiation oncology for optimal local therapy. Surgery will assess optimal timing of rebiopsy during their evaluation of patient once neoadjuvant therapy is complete.
8. See section 11

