#### 7.2.3.1 Response by RECIST criteria

After 8 weeks of Cetuximab has been completed, the patient will have a restaging CT scan with IV contrast for comparison to the first CT scan performed prior to neoadjuvant cetuximab. CT response will be evaluated using RECIST criteria for partial response versus progressive or stable disease ( Eisenhauer et al. 2009). The RECIST criteria will be applied to the combination of primary site and associated neck lymphadenopathy.

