## **15. Statistical Considerations**

### **15.1 Primary Hypothesis**

We hypothesize that the response rate to cetuximab is greater than 10%.

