### **15.2 Sample Size Justification**

Sample size was justified based on the primary hypothesis. We expect the response rate is 30%. With 20 patients, the one-sided Binomial exact test at a significance level 0.05 (actual Type I error = 4.32%) will achieve 76.2% power when true response rate is 30%.

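### Tissue taken at the pre-treatment biopsy can count as RECIST shrinkage, because the biopsy type is inconsistent and its order relative to the baseline CT is not set

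*Combined protocol and SAP*

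**What the plan says.** **Biopsy type.** Tissue sampling is a condition of entry (5.1.3). For the pre-treatment sample, 11.2 says that all patients "will have an incisional/core biopsy from the primary site and a skin punch biopsy", and it favours incisional over core. The schedule in Section 6 also lists incisional or core. Section 7.2.1 prefers core to fine-needle aspiration. Section 11.3, which gives the handling steps and names no timepoint, says "Incisional or excisional biopsy will be obtained from the primary site and BRS notified". Excisional biopsy appears nowhere else.

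**Timing.** Section 6 allows the tumour biopsy and the baseline imaging each within 30 days of treatment; footnote 5 describes the imaging as "to be obtained no more than 1 month prior to cetuximab". No rule orders the two. Section 7.2.1 describes staging by imaging first and the biopsy second, without requiring that sequence.

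**Endpoint.** Under 7.2.3.1 the post-treatment CT is taken "for comparison to the first CT scan performed prior to neoadjuvant cetuximab", and RECIST is applied to the primary site and the neck nodes together. Sections 7.2.3.1, 9 and 9.2 have no rule for a target lesion that has been cut into or removed.

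**Test.** Section 15.1 states "We hypothesize that the response rate to cetuximab is greater than 10"%. Section 15.2 says that the one-sided exact test with 20 patients "will achieve 76.2% power when true response rate is 30"%.

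**The concern.** The baseline measurement should describe the lesion as it stands when the drug starts. Here a patient may have the CT, then lose part of the primary to the biopsy, then start cetuximab, and the loss is measured as change from baseline. One pre-treatment biopsy has to supply pathology, genomic profiling, RNA sequencing, Western blot and immunohistochemistry, which favours generous samples.

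Response is the only endpoint with a formal test, and there is one arm, so no control group would show the same artefact. The direct effect of removing tissue is towards response. At the extreme, a sole target lesion removed entirely would meet the plan's definition of complete response, the disappearance of all target lesions, before any drug was given.

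**Working it through.** **1. The plan's own figures.** Inputs from 15.1 and 15.2: n = 20, null rate 0.10, expected rate 0.30, one-sided exact binomial test at 0.05.
- P(X ≥ 4 | 20, 0.10) = 13.3%, above 5%.
- P(X ≥ 5 | 20, 0.10) = 4.32%, so five responses are needed. This matches the stated error.
- P(X ≥ 5 | 20, 0.30) = 76.2%, which matches the stated power.

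The sample-size arithmetic is correct. The point concerns what gets counted as a response.

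**2. How much length has to go.** Partial response needs a 30% fall in the sum of longest diameters.
- Single 20 mm target: 0.30 × 20 = 6 mm.
- Single 11 mm target (9.2 accepts lesions just over 10 mm): 0.30 × 11 = 3.3 mm.
- Assumed 20 mm primary plus 20 mm node: 0.30 × 40 = 12 mm.

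Only loss along the longest diameter counts, and extra target lesions dilute it. A core biopsy would rarely come near these values. A large incisional biopsy of a small single lesion could, and an excisional one would.

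**3. Removal need not reach 30% by itself.** Take a 20 mm lesion on CT, 4 mm removed along its longest diameter at biopsy, and 14 mm on the post-treatment CT.
- Against the pre-biopsy CT: (20 − 14)/20 = 30%, a partial response.
- Against the post-biopsy lesion: (16 − 14)/16 = 12.5%, stable disease.

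**4. Effect on the test.** The documents give no frequency, so these are illustrations with a true rate of 10%.

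(a) If k patients are scored responders because of biopsy, the error is P(X ≥ 5 − k | 20 − k, 0.10).

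| k | One-sided error |
|---|---|
| 0 | 4.3% |
| 1 | 11.5% |
| 2 | 26.6% |

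(b) If biopsy adds d percentage points to the response rate, the error is P(X ≥ 5 | 20, 0.10 + d).

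| d (points) | One-sided error |
|---|---|
| 0 | 4.3% |
| 2 | 8.3% |
| 5 | 17.0% |
| 10 | 37.0% |

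**The case against.** The strongest reply is that the total-removal case rests on one word. Every provision specific to the pre-treatment sample (Section 6, 7.2.1, 11.2) leaves excision out. Section 11.3 names no timepoint, so its excisional option may describe tissue taken at surgery. One might try to tie 11.3 to the pre-treatment sample because it sends the block to FoundationOne, and 11.2 says post-treatment tissue does not go there. But 11.1 lists FoundationOne on samples at definitive local treatment as well, so the documents conflict. Removing the whole tumour beforehand would also sit oddly with a study meant to shrink tumours before surgery. This stands: a reader might infer that the plan intends pre-treatment excision and will create complete responses before any drug, and the documents do not support that.

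It also stands that a core or small incisional biopsy would rarely move the sum by 30%, and that nothing in the documents supports any particular nonzero frequency.

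A reader might take 2 cm as the entry minimum and 6 mm as the smallest loss that matters. Section 5.1.1 offers 2 cm as one of several criteria joined by *and/or*, so no minimum size applies to all patients.

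Finally, this is a pilot with safety and feasibility as a co-primary aim, and Section 6 already schedules a tumour-site assessment and photographs within 14 days of treatment. These lower the stakes and make a repair easier. They do not close the gap, because nothing requires that assessment to follow the biopsy or links it to the response baseline.

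**Conclusion.** The gap is real but narrower than total removal. The biopsy type is inconsistent across sections, the order of biopsy and CT is open, and the baseline is the first CT whatever happens to the lesion afterwards. Followed literally, the text can credit tissue removal to cetuximab in the only tested endpoint. The exposure is mainly to excisional or large incisional biopsies of small or single target lesions when the CT precedes the biopsy.

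The size is conditional. One affected patient of 20 takes the one-sided error from 4.3% to 11.5%; 2, 5 or 10 added percentage points give 8.3%, 17.0% or 37.0%. A reader might infer that the trial's error rate is in fact inflated. The documents do not support that, since they allow the sequence without requiring it and give no frequency. Nor is the error strictly one-directional, because healing tissue could hide some true shrinkage. The point merits a correction because five responses decide the test and the repair is cheap.

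**What to change.** 1. **Reconcile the biopsy type** across Section 6, 7.2.1, 11.1, 11.2 and 11.3, and state which timepoint 11.3 covers.
2. **Define the baseline** in 7.2.3.1 and 9.2. A lesion removed by biopsy cannot be a target lesion, and the baseline sum describes the lesions after biopsy. Use a CT taken after the biopsy where the existing window allows this without an extra scan. Otherwise record the biopsy date, the length removed and the post-biopsy longest diameter at the tumour-site assessment already scheduled within 14 days of treatment, done after the biopsy.
3. **Pre-specify a sensitivity analysis.** Where the only baseline CT precedes the biopsy, recompute percent change from the CT baseline less the length removed along the longest diameter. Count as non-responders those who do not reach a 30% decrease on that basis. A rule that drops only patients whose total shrinkage is no larger than the tissue removed would not do: in step 3 of the working, 6 mm exceeds 4 mm, so that patient would stay a responder.

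**Cost.** Some wording and a few eCRF fields. Swelling soon after biopsy may enlarge a post-biopsy CT baseline, and its resolution would then look like response, so the biopsy-to-CT interval should be recorded and reported. Section 7.2.1 makes the nodal biopsy depend on finding nodal disease, so a CT after every biopsy will not always be possible; hence the fallback in item 2. If all 20 patients keep a target lesion, the design stays at 4.32% and 76.2%. If one is left with none, five responses are still needed from the other 19, and power falls to 71.8% (error 3.5%). The plan should say in advance how such a patient is counted.

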### 7.2 Sequence of treatment

#### 7.2.1 Prior to neoadjuvant cetuximab

Patients will be staged using imaging to delineate the extent of disease. Initial biopsy specimen (preferably a core biopsy as opposed to a FNA) will be procured from the primary cutaneous site. If the patient is found to have regional lymph node involvement, core biopsy of accessible node will also be obtained. Samples will be used for confirmation of diagnosis as well as DNA and RNA genotyping. These specimens will be flash frozen and brought that same day to the Biospecimen Repository Service (BRS).

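### As worded, Section 11.3 assigns no paraffin tumor or skin tissue to immunohistochemistry, although 11.1 and 11.2 call for it

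*Combined protocol and SAP*

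**What the plan says.** Section 1.2 lists molecular correlates among the secondary objectives. Two of its four bullets compare tumor tissue before and after treatment, one for activated caspase-3 and one for ADCC.

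Section 11.1 places "Analysis of ADCC and caspase by IHC" second in its priority list, after FoundationOne and ahead of RNA sequencing. Its text says the work will be done "using paraffin embedded tissue from pre- and post- treatment samples". Item 4 of Section 11.2 widens the need: "Providing FFPE tumor and skin tissue for use in IHC analysis".

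Section 11.3 then says where the tissue goes:

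- Step 3a: pathology embeds one portion of the tumor and takes some of that block for diagnosis. As to what is left, "the remainder of the paraffin embedded block will be sent to FoundationOneTM".
- Step 3b: another part of the tumor goes on dry ice to the genomics facility.
- Step 3c: "The skin sample will be logged in, put in dry ice and sent asap to Cancer Institute Genomic Facility". The same step says of the skin sample that "its purpose is solely to investigate etiology of the cetuximab folliculitis".

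Sections 7.2.1 (before cetuximab) and 7.2.4 (after) describe the specimens only as flash frozen and taken to the biospecimen repository the same day. Section 11.2 adds that post-treatment tumor is for RNA sequencing alone and does not go to FoundationOne.

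**The concern.** The sections that state the need and the section that distributes the tissue disagree. Steps 3a and 3c of 11.3 are routing instructions, not mere silence: one disposes of the block between two users, and the other sends the skin sample in one piece to a frozen-tissue destination. Staff who follow them have no instruction to hold any paraffin material for the second-ranked assay.

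At stake are the paired caspase-3 and ADCC comparisons. A pair needs a baseline member, and none is assigned. Whether tissue is fixed or frozen is decided at collection, whereas funding for IHC may be settled later (Section 17), so an omission at collection may not be recoverable once money is found.

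**Working it through.** The point is not numerical, so the check follows each tissue type from the stated need to the stated destination.

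| Tissue | Paraffin for IHC asked for in | Stated destination | Share assigned to paraffin IHC |
|---|---|---|---|
| Tumor, before cetuximab | 11.1 text; 11.2 item 4 | 11.3(3a): diagnosis, rest of block to FoundationOne. 11.3(3b): dry ice to genomics. 7.2.1: flash frozen | None |
| Tumor, after cetuximab | 11.1 text; 11.2 item 4 | 11.2: RNA sequencing alone, not FoundationOne. 7.2.4: flash frozen | None |
| Skin, before and after | 11.2 item 4 only | 11.3(3c): sample on dry ice to genomics | None |

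**Baseline tumor.** The two uses in 3a account for the whole block as worded, and the other portion named, in 3b, is frozen. With 20 planned patients (4.1, 15.2) and one pre-treatment tumor biopsy each, 20 × 1 = 20 samples, of which 0 are assigned to IHC.

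**Post-treatment tumor.** The obstacle here is different. Section 11.2 says this tissue does not go to FoundationOne, so the block-remainder rule does not explain the gap. The sentence limiting the tissue to RNA sequencing does, and it contradicts the post-treatment IHC in 11.1. It also conflicts with item 1 of 11.1, which lists a FoundationOne profile before or at definitive local treatment.

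**Skin.** Section 11.2 calls for a punch before and after cetuximab, so 20 × 2 = 40 samples at most, of which 0 have a fixed portion under 3c. The further skin biopsy that the Section 6 schedule lists after failure is not counted. Section 11.1 does not name skin IHC; that need rests on 11.2 item 4.

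**Pairs.** With 0 assigned baseline tumor samples, 0 of up to 20 caspase-3 or ADCC pairs have an assigned baseline member. These zeros count what the wording assigns; they do not predict what pathology would actually retain.

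**Effect on the main design.** The plan's own calculation does not depend on this tissue, and it reproduces. With success defined as at least 5 responses in 20, P(X ≥ 5 | n = 20, p = 0.10) = 0.0432, against the stated 4.32%, and P(X ≥ 5 | n = 20, p = 0.30) = 0.7625, against the stated 76.2%.

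**The case against.** The strongest reply is that a missing allocation is not a missing specimen. Section 11.3 speaks of a block, not the sole block; it does not forbid keeping sections, making a second block or having the block returned. It has the repository transporting research specimens of unstated type, and Section 2.1 expects tumors to be banked. Text that follows the 11.3 list was not available for this review and may hold further handling steps. All of this stands. A reader might infer that the IHC cannot be run; the documents support only that no share is assigned. Even so, a later step reserving tissue would conflict with 3a and 3c until those sentences are reworded.

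The need is also softer than a requirement. Section 11.1 presents its list as possible investigations, Section 1.2 frames the goals as exploratory, and Section 17 makes IHC depend on funds. That limits the importance of the point but does not remove the contradiction.

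Three further inferences are tempting and should not be drawn:

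- *That patients undergo biopsies for assays that cannot be done.* The same tissue serves FoundationOne, RNA and DNA sequencing and Western blot.
- *That 7.2.1 leaves no paraffin even for FoundationOne.* It is a short description, the same paragraph uses the samples to confirm diagnosis, and the Section 6 schedule refers readers to Section 11 for the biopsies.
- *That rash assessment needs fixed skin.* Section 7.3.3.1 mentions a histologic feature descriptively, but folliculitis is graded clinically by CTCAE, and 11.3 says the skin sample needs no pathologic diagnosis.

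**Conclusion.** The inconsistency is real and worth correcting. On the visible wording, 11.3 assigns no paraffin tissue to IHC, contrary to 11.1 and to item 4 of 11.2. The baseline gap comes from 3a, the post-treatment gap from the RNA-only sentence in 11.2, and the skin gap from 3c. The skin conflict is the plainest, because 3c describes the sample as going to one place undivided.

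The size is 0 of up to 20 baseline tumor samples and 0 of up to 40 skin punches assigned, on a literal reading and assuming that all 20 planned patients give every sample. The conclusion does not depend on the unavailable text being silent: it rests on the words of 3a and 3c. It reaches only exploratory, funding-dependent correlates. The response endpoint, the sample size and the stated power are untouched.

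**What to change.** 1. In 11.3(3a), have pathology keep unstained sections, or a second block, for caspase-3 and ADCC IHC whenever the tissue is sufficient for FoundationOne, and send the rest. FoundationOne keeps first call, as 11.1 ranks it. Record the patients in whom nothing could be kept, so that the number of evaluable pairs is known. The documents give no tissue yields, so pathology should set the number of sections.
2. In 11.3(3c), either fix a portion of each skin punch for IHC or, if skin IHC is not intended, remove skin from item 4 of 11.2.
3. In 7.2.1 and 7.2.4, say that specimens are divided as set out in 11.3.
4. Reconcile the 11.2 sentence limiting post-treatment tumor to RNA sequencing with the post-treatment IHC in 11.1 and with the FoundationOne time points in 11.1, item 1.
5. State in 11.3, for each time point, which portions of tumor and skin are fixed and which are frozen.

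The cost is protocol and laboratory wording and some section cutting, with no extra biopsy. The downside is slightly less tissue for FoundationOne and RNA sequencing and, if punches are divided, less frozen skin.
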